#### **10.13.4 Amended protocol 01 (07 April 2022)**

This amended protocol (amendment 01) is considered to be substantial based on the criteria set forth in Article 10(a) of Directive 2001/20/EC of the European Parliament and the Council of the European Union.

### **OVERALL RATIONALE FOR THE AMENDMENT**

The main purpose of the protocol amendment 01 is to provide monthly pregnancy test for female participants of childbearing potential, to modify the criterion for IMP reinitiation, and to address health authority requests.

**Protocol amendment summary of changes table**

Section # and Name	Description of Change	Brief Rationale
Title Page	Updated IND number from: 15444 To: 151444.	Error correction
Title Page	Updated NCT number as NCT05237284.	Update
1.1 Synopsis (Main Secondary; endpoints in Part A); 3 Objectives and Endpoints (Part A); 9.4.3 Secondary endpoint(s) in Part A; 10.8.1.1 Study objectives and endpoints (Part A)	Clarify the secondary endpoint, muscle strength will be analyzed as the change from baseline to Week 24.	Clarification
1.1 Synopsis (Brief summary and Intervention groups and duration); 4.1 Overall design; Part A	Reworded to clarify that All ongoing participants in Part A will rollover to Part B.	To clarify the request for participants to rollover from Part A to Part B
1.1 Synopsis (Brief summary); 4.1 Overall design; Part B	Reworded to clarify that participants who permanently discontinue IMP in Part A will not receive SAR443820 in Part B.	Clarification
1.1 Synopsis (Rationale); 2.1 Study Rationale	The text "In summary, both preclinical and clinical studies have affirmed RIPK1 is a key mediator of necroptosis and inflammatory pathways in ALS." has been modified to "In summary, both preclinical and patient-derived data have suggested RIPK1 may be a key mediator of necroptosis and inflammatory pathways in ALS."	To be specific on the evidence supporting the study rationale
1.1 Synopsis (Intervention groups and duration); 2.3.3 Overall benefit/risk conclusion; 6.8 Concomitant therapy	Updated from "November 2021" to "April 2022" on the available standard of care.	Update
1.3 Schedule of Activities, Part A	Instruction on IMP dosing at Week 24 has been added in footnote a (Part A).	Clarification

Section # and Name	Description of Change	Brief Rationale
1.3 Schedule of Activities Part A; 8.2.3 Vital signs	Footnote 'j' added and details in Section 8.2.3 was reworded to provide instruction on when vital signs will be measured after first dose of IMP on Day 1.	Clarification
1.3 Schedule of Activities, Part A and Part B	In footnote b (Part A) and footnote c (Part B), 'discontinue from the study early' has been replaced by 'prematurely discontinue IMP'.	To clarify the participants who are required to take early discontinuation visit
1.3 Schedule of Activities, Part A and Part B; 8.2.6 Pregnancy testing	New footnote 'o' (Part A) and footnote 'l' (Part B) have been added to include instructions on pregnancy test.	To increase pregnancy test frequency to monthly since complete definite embryo-fetal study results are not available yet
1.3 Schedule of Activities, Part A	Procedure 'HHD' was replaced with 'Muscle strength' and a new footnote 'q' (Part A) have been added to include instructions on measuring muscle strength.	Adding hand grip in the muscle strength measurement
2.3.1 Table 1 Risk assessment	Summary of data/rationale for risk related to convulsion was updated to include following text: No convulsions have been observed up to the dose level of [REDACTED] mg/kg/day in both the 3-month and 9-month studies.	Preclinical data update
	Mitigation strategy for convulsion was updated to include The following text: participants weighing <45 kg.	Clarification
	Summary of data/rationale for risk related to Immunomodulatory Effects was updated to include "9-month" for the nonhuman primate studies.	Preclinical data update
2.3.3 Overall benefit/risk conclusion	[REDACTED]	Updated with reference to completed first-in-human Phase 1 study result
3 Objectives and Endpoints, Part B	'Week 102' has been corrected to 'Week 104'.	Correction of typographical error
5.2 Exclusion Criteria	The following text has been added to E 03: "other causes of neuromuscular weakness"	Clarification
	The following text has been added to E 12: "(eg, sodium phenylbutyrate and/or taurursodiol)".	Clarification
5.3.1 Meals and dietary restrictions	Information was updated to clarify that participants should be prohibited from consuming grapefruit and grapefruit juices from 5 days before the start of the study intervention until 2 days after the final dose.	To avoid effect of grapefruit on SAR443820 metabolism as SAR443820 is mainly metabolized by CYP3A4 and grapefruit is a strong inhibitor of CYP3A4
6.1 Study Intervention(s) Administered	The instruction on drug administration has been modified to add details on the volume of water to use and how to mix the tablet with water.	To keep the instruction on drug administration

Section # and Name	Description of Change	Brief Rationale
		consistent between protocol and pharmacy manual
7.1.1 Permanent Discontinuation	
Initiation of riluzole and/or edaravone during Part A was added as one of the criteria for study discontinuation.
 
The text in "Handling of participants after permanent intervention discontinuation" was updated to clarify that participants who prematurely discontinue the IMP will be encouraged to continue the rest of study visits for safety and efficacy assessments up to the last scheduled visit.
	
To emphasize the criteria of study discontinuation
 
To be aligned with the intent-to-treat (ITT) analysis strategy

7.1.2.1 Study intervention restart or rechallenge after temporary discontinuation of study intervention	
Any content related to the request of Sponsor approval to restart/rechallenge IMP has been deleted
 
If required "based on local practice" has been added after "Ethics Committee and/or Institutional Review Board (IRB) approval is obtained"
 
"In case of confirmed liver injury caused by the IMP, the rechallenge with the IMP is not permitted and the participants must be permanently discontinued from IMP treatment." has been added.
	
To be aligned with ICH GCP guidance that investigator is responsible for all trial-related medical decisions
 
To provide flexibility on the request of IRB approval
 
To emphasize confirmed IMP-induced liver injury will lead to permanent discontinuation of IMP

8.1.3 Muscle strength measurement	Heading title for Section 8.1.3 updated from "Handheld dynamometry (HHD)" to "Muscle strength measurement and the following text of "Bilateral hand grip will be measured using a grip dynamometer and all other muscles included in this study will be measured using a handheld dynamometer." was added	Adding hand grip in the muscle strength measurement
8.3.7 Disease-related events and/or disease-related outcomes not qualifying as AEs or SAEs	Disease-related events and disease-related outcomes have been defined and examples provided.	Clarification
8.3.8 Adverse event of special interest	
The criterion of overdose has been updated.
 
Reworded to clarify two AESI: serious infection and ALT increase.
	
Correction of error
 
Clarification

8.5 Genetics and/or pharmacogenomics	Added following text for an optional blood collection for isolation of DNA: "single".	Clarification
8.6 Biomarkers	Sample storage period was updated from '15 years' to '5 years' when the samples will be used only for clinical study related testing.	To clarify how long the sample will be stored for the clinical study related testing
8.9 Use Of Biological Samples And Data For Future Research	Reworded to clarify the purpose of future research.	Clarification
9.1 Statistical Hypothesis	Added new section to explain the statistical hypothesis.	To provide clarity on statistical hypothesis based

Section # and Name	Description of Change	Brief Rationale
		on request from Pharmaceuticals and Medical Devices Agency in Japan
	"The study will be declared positive if the null hypothesis for the primary endpoint in Part A change from baseline in the ALSFRS-R total score to Week 24 (end of Part A) for SAR443820 versus placebo is rejected in the primary analysis." has been added.	To add declaration of success
9.5 Interim Analyses	Added text to clarify when interim analysis will be conducted.	To provide clarity on interim analysis
10.1.7 Data quality assurance	Added description on how quality tolerance limits (QTLs) will be managed in the study.	Clarification
10.6 Appendix 6	Instructions on ALT increase have been added following the "Increase in ALT algorithm".	To provide detailed instruction on ALT increase
10.11 Appendix 11	Added a new appendix for blood volume details.	Clarification
Throughout the document	Editorial changes.	Grammatical corrections

3.4.3 Comparison with external control.....	25
3.5 MULTIPLICITY ISSUES	26
3.6 SAFETY ANALYSES	27
3.6.1 Extent of exposure	28
3.6.2 Adverse events	29

3.6.3	Additional safety assessments.....	32
3.6.3.1	Laboratory variables, vital signs and electrocardiograms (ECGs).....	32
3.6.3.2	Analysis of suicidality assessment.....	34
3.7	OTHER ANALYSES	34
3.7.1	Other variables and/or parameters	34
3.7.1.1	Pharmacokinetic (PK) analyses	34
3.7.1.2	Pharmacodynamic (PD) analyses.....	34
3.7.1.3	PK/PD analysis	35
3.8	INTERIM ANALYSES	35
3.9	CHANGES TO PROTOCOL-PLANNED ANALYSES.....	35
4	SAMPLE SIZE DETERMINATION	37
5	SUPPORTING DOCUMENTATION	38
5.1	APPENDIX 1 LIST OF ABBREVIATIONS	38
5.2	APPENDIX 2 PARTICIPANT DISPOSITIONS	38
5.3	APPENDIX 3 DEMOGRAPHICS AND BASELINE CHARACTERISTICS, PRIOR OR CONCOMITANT MEDICATIONS	40
5.4	APPENDIX 4 DATA HANDLING CONVENTIONS	42
6	REFERENCES.....	47

LIST OF TABLES

Table 1 - Objectives and endpoints.....	7
Table 2 - Summary of primary estimand for main endpoints	10
Table 3 - Populations for analyses	12
Table 4 - Sorting of AE tables	30
Table 5 - Analyses of adverse events	31
Table 6 - Selections for AESIs	32
Table 7 - Analyses window definition of efficacy variables	42
Table 8 - Analyses window definition of safety variables.....	43
Table 9 - Analyses window definition of PD variables.....	45

VERSION HISTORY

This amended statistical analysis plan (SAP) for study ACT16970 is based on the Amended Clinical Trial Protocol 05 dated 13-Dec-2023. The first participant was randomized on 28-Apr-2022. The initial SAP V1 was approved before the interim analysis for futility was conducted. This amended SAP is approved before the first database lock.

Major changes in statistical analysis plan

SAP Version	Approval Date	Changes from Protocol Amendment	Rationale
1	28-Apr-2023	
Disease duration (from first symptom onset to the screening visit) and the corresponding by-visit interaction are added as covariates in the Part A primary analysis model.
 
[REDACTED]. Instead, each of the 5 dimensions will be included in the analysis.
	Based on clinical input Index score is not really used for regulatory/clinical development purposes
2	08-Jan-2024	
MMRM will be applied to the complete datasets after multiple imputation instead of ANCOVA in the sensitivity analysis of the primary endpoint in Part A.
 
[REDACTED]
 
Update megascore derivation if there are missing measurements
 
Add the analysis of grip strength and its derivation
	Based on FDA feedback Based on FDA feedback Clarification Clarification
Additional changes have been made to improve clarity and consistency.			

1 INTRODUCTION

1.1 STUDY DESIGN

This is a Phase 2, multicenter, randomized, double-blind, placebo-controlled, 2 parallel-group study to evaluate the efficacy and safety of SAR443820 in adult participants with amyotrophic lateral sclerosis, followed by an open-label extension.

Part A is a 24-week, double-blind, placebo-controlled part, preceded by a screening period of up to 4 weeks before Day 1. After a screening phase of up to 4 weeks, participants will be randomized in a ratio of 2:1 to receive 20 mg BID SAR443820 (n=174) or placebo BID (n=87). Randomization will be stratified by the geographic region of the study site (Asia, Europe or North America), region of ALS onset (bulbar or other areas), use of riluzole (yes or no), use of edaravone (yes or no), and use of the combination of sodium phenylbutyrate and taurursodiol (named Relyvrio in the USA and Albrioza in Canada) (yes or no). Participants will attend in-clinic study assessments at baseline (Day 1), Week 2, Week 4, Week 6, Week 8, Week 10, Week 12, Week 16, Week 20 and Week 24. All ongoing participants at Week 24 will rollover to open-label extension Part B. Participants who discontinue the treatment or choose not to enter Part B will have their follow up visit 2 weeks after the last dose of the study intervention.

Part B is an open-label, long-term extension of Part A, which starts from Week 24 and continues up to Week 106. The study intervention assignment of participants at randomization in Part A will remain blinded to Investigators, participants, and site personnel until the end of Part B unless there is medical need to unblind the study intervention assignment. All participants will receive 20 mg BID SAR443820 in Part B starting from Week 24, except those who discontinue IMP treatment permanently in Part A. Based on a data review, and in accordance with Data Monitoring Committee (DMC) recommendations, sites have been instructed on 5th December 2023 to pause the administration of SAR443820 in Part B (open-label extension) immediately. All participants in Part B will be encouraged to continue follow-up visits, but no doses of SAR443820 should be administered. Rollover to Part B for follow-up visits after completing Part A is also encouraged, but without taking SAR443820 in Part B. The decision of whether resuming SAR443820 administration in Part B will be made based on DMC recommendation when Part A data is available and benefit risk evaluation is made.

The study duration includes an up to 4-week screening period, 24-week double-blind treatment period in Part A, 80-week open-label treatment period (Part B) and 2-week post-treatment follow-up period, with a maximum total study duration of 110 weeks.

1.2 OBJECTIVES AND ENDPOINTS

Table 1 - Objectives and endpoints

Part A

Objectives	Endpoints
Primary	

 • To assess the effect of SAR443820 compared to placebo in reducing ALS progression as measured by the Amyotrophic Lateral Sclerosis Functional Rating Scale Revised (ALSFRS-R) 	
 • Change from baseline in the ALSFRS-R total score to Week 24
Secondary	

 • To assess the effect of SAR443820 compared to placebo on a combined assessment of function and survival, respiratory function, muscle strength, and quality of life (QoL) 	
 • Combined assessment of the function and survival (CAFS) score at Week 24
	
 • Change from baseline in slow vital capacity (SVC) to Week 24
	
 • Change from baseline in muscle strength to Week 24
	
 • Change from baseline in Amyotrophic Lateral Sclerosis Assessment Questionnaire (ALSAQ-5) to Week 24
	
 • Change from baseline in serum neurofilament light chain (NfL) to Week 24
	
 • Incidence of adverse events (AE), serious adverse events (SAE), treatment-emergent adverse events (TEAE), potentially clinically significant abnormalities (PCSA) in laboratory tests, electrocardiogram (ECG), and vital signs over 24 weeks
	
 • Plasma concentration of SAR443820

Objectives	Endpoints
	[REDACTED]
	[REDACTED]

• To assess the effects of SAR443820 compared to placebo on neurodegeneration and inflammation disease biomarkers	
• Change from baseline in soluble triggering receptor expressed on myeloid cells-2 (sTREM2) in plasma chitinase-3-like protein-1 (CHI3L1), a selected panel of cytokines and chemokines in serum, and extracellular domain of p75 (p75ECD) in urine to Week 24

Part B

Objectives	Endpoints
Primary	

• To assess the long-term effects of SAR443820 on function and survival	
• Combined assessment of the function and survival (CAFS) score at Week 52
Secondary	

1.2.1 Estimands

Primary estimands defined for main endpoints in Part A are summarized in below [Table 2](#). More details are provided in [Section 3](#).

For all these estimands, the comparison of interest will be the comparison of SAR443820 vs. placebo.

Table 2 - Summary of primary estimand for main endpoints

Endpoint Category (estimand)	Estimands				Population-level summary (Analysis and missing data handling)
	Endpoint	Population	Intercurrent event(s) handling strategy		
Primary objective: To assess the effect of SAR443820 compared to placebo in reducing ALS progression as measured by the Amyotrophic Lateral Sclerosis Functional Rating Scale Revised (ALSFRS-R)					
Primary endpoint (treatment policy)	Change from baseline in the ALSFRS-R total score to Week 24	ITT	Permanent study intervention discontinuation before Week 24 – regardless of treatment discontinuation (treatment policy)		The primary endpoint will be analyzed using MMRM with change from baseline in ALSFRS-R total score up to Week 24 as response variable, and treatment, visit, randomization strata of the geographic region of the study site, ALS onset region (bulbar or other areas), use of riluzole (yes or no), use of edaravone (yes or no), use of the combination of sodium phenylbutyrate and taurursodiol (yes or no), treatment-by-visit interaction, disease duration (from first symptom onset to the screening visit), baseline ALSFRS-R score, baseline NfL, disease duration-by-visit interaction, baseline NfL-by-visit interaction and baseline ALSFRS-R score-by-visit interaction as covariates. All available data will be used, and missing data will be handled by MMRM based on missing at random assumption.
Secondary endpoints (treatment policy)	Combined assessment of the function and survival (CAFS) score at Week 24	MITT	Permanent study intervention discontinuation before Week 24 – regardless of treatment discontinuation (treatment policy)		CAFS at Week 24 will be analyzed using the Wilcoxon-Mann-Whitney test to compare mean scores between the treatment groups at Week 24.
	Change from baseline in slow vital capacity (SVC) (muscle strength, Amyotrophic Lateral Sclerosis Assessment Questionnaire (ALSAQ-5), serum neurofilament light chain (NfL)) to Week 24	ITT	Permanent study intervention discontinuation before Week 24 – regardless of treatment discontinuation (treatment policy)		These secondary endpoints will be analyzed using MMRM with change from baseline value up to Week 24 as response variable, and treatment, visit, randomization strata of the geographic region of the study site, ALS onset region (bulbar or other areas), use of riluzole (yes or no), use of edaravone (yes or no), use of the combination of sodium phenylbutyrate and taurursodiol (yes or no), treatment-by-visit interaction, disease duration (from first symptom onset to the screening visit), baseline value of the endpoint, baseline NfL (if different from the baseline value of the endpoint), disease duration-by-visit interaction, baseline value of the endpoint-by-visit interaction and

Endpoint Category (estimand)	Endpoint	Population	Intercurrent event(s) handling strategy	Estimands	Population-level summary (Analysis and missing data handling)
				baseline NfL-by-visit interaction (if different from the baseline value of the endpoint-by-visit interaction) as covariates. All available data will be used, and missing data will be handled by MMRM based on missing at random assumption. For muscle strength data, if there is a missing value for one muscle measurement which continues to have the missing value through the final assessment (eg, at least 2 consecutive missing values up to the final assessment), then these missing values for this muscle measurement will be imputed as zero; all the other missing values will not be imputed.	

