3.2.2 Main analytical approach

Part A

The primary endpoint in Part A will be analyzed with the estimand defined according to the following attributes:

- Endpoint: Change from baseline in the ALSFRS-R total score to Week 24
- Treatment condition: SAR443820 will be compared to placebo
- Analysis population: ITT population
- Intercurrent events (IE):
 - The IMP discontinuation IE will be handled with the treatment policy strategy; The primary endpoint will be assessed based on all assessments irrespective of the IMP discontinuation
- Population-level summary: The primary endpoint will be analyzed using MMRM with change from baseline in ALSFRS-R total score up to Week 24 as response variable, and treatment, visit, randomization strata of the geographic region of the study site, ALS onset region (bulbar or other areas), use of riluzole (yes or no), use of edaravone (yes or no), use of the combination of sodium phenylbutyrate and taurursodiol (yes or no), treatment-by-visit interaction, disease duration (from first symptom onset to the screening visit), baseline ALSFRS-R score, baseline NfL, disease duration-by-visit interaction, baseline NfL-by-visit interaction and baseline ALSFRS-R score-by-visit interaction as covariates. If less than 10 participants in a randomization strata level, then the corresponding factor will not be included as a covariate in the MMRM model.

The least squares mean difference in the ALSFRS-R change from baseline at Week 24 between SAR443820 vs placebo, together with the p-value and the 95% CI for the difference, will be estimated from the MMRM model using weights for each stratum equal to the overall proportion of participants in each stratum (ie, “population weight”) by inclusion of the OBSMARGINS option in the LSMEANS statement. Plots of least squares means (\pm standard error) over time will be provided.

This model will be implemented using the SAS MIXED procedure with an unstructured covariance matrix to model the within-participant errors. Parameters will be estimated using the restricted maximum likelihood method. The denominator degrees of freedom will be estimated using the Kenward-Roger approximation. This model will provide baseline adjusted least-squares means estimates at Week 24 for SAR443820 and placebo, together with their corresponding standard errors and CIs. If this model fails to converge, the following variance-covariance structures will be tested in this order:

- Heterogeneous Toeplitz
- Heterogeneous AR(1)

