3.2.3 Sensitivity analyses

3.2.4 Supplementary analyses for primary endpoint in Part A

To assess the treatment effect when the participants adhere to the study treatment as directed, the difference (SAR443820 vs placebo) in the mean change from baseline in the ALSFRS-R total score to Week 24 will be analyzed in the ITT population based on data collected during the treatment-emergent period for the Part A using the same model as primary analysis. ALSFRS-R total scores obtained after the IMP discontinuation will be considered as missing.

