3.3.1.2 Main analytical approach

Treatment policy will be used for the analyses of all secondary endpoints in Part A and Part B as stated in [Table 2](#).

CAFS

CAFS at Week 24, Week 76 and Week 104 will be analyzed in the same manner as that used to analyze the primary endpoint in Part B in [Section 3.2.2](#).

Continuous Endpoints

Continuous endpoints include:

Part A

- change from baseline in SVC to Week 24
- change from baseline in muscle strength to Week 24
 - change from baseline in megascore to Week 24
 - change from baseline in grip strength to Week 24
- change from baseline in ALSAQ-5 to Week 24
- change from baseline in serum NfL to Week 24

Part B

- change from baseline in the ALSFRS-R total score to Week 52, Week 76, and Week 104
- change from baseline in SVC to Week 52, Week 76, and Week 104
- change from baseline in ALSAQ-5 to Week 52, Week 76, and Week 104
- change from baseline in serum NfL to Week 52

These continuous endpoints will be analyzed using the same manner as that used to analyze the primary endpoint in Part A in [Section 3.2.2](#), except that baseline ALSFRS-R score will be replaced by the baseline value of the corresponding endpoint. Plots of least squares means (\pm standard error) over time will be provided. Plots of mean (\pm SD) and/or mean change (\pm SD) and/or median over time will also be provided. For NfL data, log transformation will be applied in

the MMRM model. The treatment difference will then be back-transformed to the original scale. The back-transformed LS means stand for geometric mean ratios compared to baseline, and the back-transformed LS means difference stands for ratio of the geometric mean ratios compared to baseline between SAR443820 and placebo. In order to assess the impact of deviation from the normality assumption, a sensitivity analysis using rank analysis of covariance (ANCOVA) with the same covariates as for the MMRM analysis except visit and related interaction terms, will be performed to provide the p-value for the comparison between the treatment groups.

Time-to-event endpoints

Time-to-event endpoints in Part B include:

[figure not shown]
- time from baseline to occurrence of either death or permanent assisted ventilation (>22 hours daily for >7 consecutive days), whichever comes first
- time from baseline to the occurrence of death

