3.3.1.3 Sensitivity analyses

CAFS endpoints in Part A and Part B

[figure not shown]
To assess the impact of baseline characteristics in the comparison of CAFS scores between treatment groups, a sensitivity analysis using a similar rank ANCOVA model to adjust for baseline prognostic factors in the mITT population as mentioned in [Section 3.2.3](#) will be performed at Week 24, Week 76 and Week 104, respectively.

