3.5 MULTIPLICITY ISSUES

To control the Type 1 error rate for the study, a hierarchical testing procedure will be applied at a 2-sided 5% significance level for primary and selected secondary endpoints in Part A, ie, each hypothesis will be formally tested only if the preceding one is significant at the 5% level. If

SAR443820 is significant for the primary endpoint in part A, a selective set of secondary endpoints in Part A will be tested following the hierarchical testing procedure shown below:

- CAFS score at Week 24
- Change from baseline in ALSAQ-5 to Week 24
- Change from baseline in serum NfL to Week 24
- Change from baseline in SVC to Week 24
- Change from baseline in megascore to Week 24

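### CAFS at Week 24, the first secondary test in the hierarchy, is the only one without covariate adjustment: valid, but it gives up power if the covariates predict CAFS

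*SAP*

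**What the plan says.** SAP 3.5 sets a fixed sequence at two-sided 5%: "a selective set of secondary endpoints in Part A will be tested following the hierarchical testing procedure shown below". The order after the primary endpoint is CAFS, ALSAQ-5, serum NfL, SVC, megascore.

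- **CAFS.** Table 2 says "CAFS at Week 24 will be analyzed using the Wilcoxon-Mann-Whitney test to compare mean scores between the treatment groups at Week 24", in the mITT population. SAP 3.3.1.2 confirms it: "CAFS at Week 24, Week 76 and Week 104 will be analyzed in the same manner" as the Part B primary endpoint, which SAP 3.2.2 tests by Wilcoxon-Mann-Whitney. Neither place mentions strata or covariates.
- **The other four secondaries.** Table 2: "These secondary endpoints will be analyzed using MMRM with change from baseline value up to Week 24 as response variable". SAP 3.3.1.2 gives them the primary endpoint's model, "except that baseline ALSFRS-R score will be replaced by the baseline value of the corresponding endpoint".
- **The primary.** SAP 3.2.2 adjusts for the five randomisation factors, disease duration, baseline ALSFRS-R and baseline NfL. It has a rule for sparse factors: "If less than 10 participants in a randomization strata level, then the corresponding factor will not be included as a covariate".
- **The adjusted CAFS analysis.** SAP 3.3.1.3 plans "a sensitivity analysis using a similar rank ANCOVA model to adjust for baseline prognostic factors in the mITT population", at Week 24 among other weeks. It takes the model from the section headed "3.2.3 Sensitivity analyses". No text stands under that heading in the available copy, so the covariate list may already be written there.

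**The concern.** CAFS combines survival with ALSFRS-R change, and the plan adjusts both components elsewhere. ALSFRS-R change is adjusted in the MMRM. Time to death or ventilation is adjusted in a Cox model with the randomisation factors, disease duration, baseline ALSFRS-R and baseline NfL (SAP 3.3.1.2). Both documents also note that faster progressors have higher NfL (Protocol 3.1.3, SAP 3.3.1.1). The plan therefore treats these variables as prognostic, yet the composite's confirmatory test uses none of them.

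Ignoring prognostic covariates does not bias a randomised comparison, but it wastes power. When the randomisation itself is stratified on prognostic factors, an unstratified rank test also becomes somewhat conservative. Because the sequence is fixed, a missed CAFS result ends formal testing of the four endpoints behind it.

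**Working it through.** **Inputs from the documents.** Two-sided 5%; N = 261, split 174:87 (SAP 1.1); about 80% power and 20% dropout for the primary (SAP 4); 3 × 2 × 2 × 2 × 2 = 48 randomisation strata (SAP 1.1); ALSFRS-R at Weeks 4, 8, 12, 16, 20 and 24 (Protocol 1.3.1); pairwise CAFS scoring (SAP 3.2.1). No power is stated for CAFS.

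**The plan's own figure.** The placebo change and SD are blacked out and N came from simulation, so 261 cannot be reproduced forward. Solving back for the standardised effect d at 80% power:

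- all randomised: d = 2.80 × √(1/174 + 1/87) = 0.368
- after 20% dropout: d = 2.80 × √(1/139.2 + 1/69.6) = 0.411

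For a 30% reduction these imply a placebo change of 0.368/0.3 = 1.23 to 0.411/0.3 = 1.37 SD.

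**Closed form.** Let R² be the share of CAFS rank variance explained by the covariates (assumed, 0 to 0.3). The Wilcoxon efficiency under normality is 0.955, and 174 × 87/261 = 58:

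adjusted power = Φ(d × √(0.955 × 58/(1 − R²)) − 1.96)

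The unadjusted test has R² = 0. With d = 0.368 it has 78.2% power throughout. The adjusted test has:

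| R² | 0 | 0.05 | 0.1 | 0.2 | 0.3 |
|---|---|---|---|---|---|
| Adjusted power, % | 78.2 | 80.2 | 82.3 | 86.5 | 90.6 |
| Gain, points | 0 | 2.0 | 4.1 | 8.3 | 12.4 |

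This formula charges nothing for fitting covariates, so the cost at R² = 0 has to come from simulation.

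**Simulation with the SAP's CAFS scoring** (8,000 replicates per cell; Monte Carlo SE about 0.25 points for type I error, 0.3 to 0.5 for power). Assumed: permuted blocks of 6 within strata; region 15/45/40%, bulbar onset 25%, riluzole 75%, edaravone 15%, sodium phenylbutyrate/taurursodiol 10%; SD 5 points; deaths about 4.5% under the null and 3.6% under the alternative; about 20% missing at Week 24; half of R² from stratification factors. Mean mITT n was 254. The primary was approximated by a Week 24 ANCOVA.

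The stated 80% can be read in two ways:

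- A: the effect is fixed at d = 0.424, which gives 80.6% primary power at R² = 0.
- B: the effect is reduced as R² rises (d = 0.399, 0.372, 0.340), so that the adjusted primary stays near 80%.

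Each cell is Wilcoxon v rank ANCOVA, in %:

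| R² | Power, A | Power, B | CAFS fails given significant primary, A | Same, B | Type I error |
|---|---|---|---|---|---|
| 0 | 84.5 v 83.6 | as A | 5.1 v 5.6 | as A | 5.2 v 5.2 |
| 0.1 | 83.6 v 86.4 | 79.3 v 82.2 | 8.0 v 5.2 | 9.5 v 6.3 | 4.6 v 4.9 |
| 0.2 | 84.2 v 90.2 | 73.8 v 81.1 | 9.7 v 4.2 | 15.4 v 7.7 | 4.1 v 5.0 |
| 0.3 | 86.0 v 94.1 | 65.7 v 79.1 | 10.4 v 2.9 | 23.3 v 9.3 | 3.7 v 5.0 |

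The gains are 2.8, 6.0 and 8.1 points (A) or 2.9, 7.3 and 13.4 points (B) at R² = 0.1, 0.2 and 0.3. At R² = 0 there is a loss of 0.9.

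**Checks.**

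- At R² = 0.3, taking 25% or 75% of R² from stratification factors gave gains (A / B) of 8.9 / 13.2 and 7.8 / 12.2. With 10% of baseline NfL missing and replaced by the pooled median, the gains were 8.6 / 13.3. Rank ANCOVA type I error stayed at 4.8 to 5.0%.
- A separate fixed-effect simulation (N = 254, 4,000 runs) gave 81.1 v 80.7%, 81.2 v 82.2%, 81.2 v 84.2%, 82.6 v 88.5% and 82.5 v 91.4% at R² = 0, 0.05, 0.1, 0.2 and 0.3.

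**The case against.** The strongest reply is that nothing is wrong. The Wilcoxon test is valid, it is the method Protocol 9.4.4 fixes for CAFS at Week 52, and the SAP uses it at every CAFS time point. Changing Week 24 alone would give one endpoint two main methods. The adjusted result will be reported anyway.

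The size of the gain also rests on assumptions. Nothing in the documents supports R² = 0.3, and eligibility narrows the prognostic range (Protocol 5.1: duration at most 2 years, slope at least 0.5 points/month, SVC at least 60%). A check with nine covariate terms (4,000 runs, Monte Carlo SE about 0.65 points) found 78.0 v 78.9% at R² = 0.05, nothing at 0.03 (79.0 v 78.9%) and a loss at 0 (78.5 v 76.9%). The CAFS failure rates above are conditional on a significant primary. Multiplied by primary power under reading A, the differences are 0.842 × 2.8 = 2.4, 0.890 × 5.5 = 4.9 and 0.936 × 7.5 = 7.0 points. Passing CAFS helps the later endpoints only if they are significant in turn.

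Timing is tight too. All participants had passed Week 19 by 5 December 2023 (Protocol amendment 05 summary), so Week 24 visits end around 9 January 2024. SAP version 2 is dated 8 January 2024.

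Much of this stands. The benefit is conditional, small below R² of about 0.05, and does not touch trial success. It does not remove the point: the plan itself treats these covariates as prognostic, the loss if they are not is about 1 point (0.4 to 1.6 across the simulations), and the adjusted model is already prespecified.

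**Conclusion.** The point holds as a low-cost improvement, not as an error. CAFS at Week 24 is the only unadjusted test in a six-step sequence and stands second in it. Across the calculations the planned rank ANCOVA gains about 3 to 4 points of power at R² = 0.1, 6 to 8 at 0.2 and 8 to 13 at 0.3. The upper end needs both R² = 0.3 and an effect scaled to keep the adjusted primary near 80%. Rank ANCOVA keeps type I error near 5%, while the Wilcoxon test drifts below it.

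The R², SD, death rates, stratum prevalences and block size are assumptions. The consequence is limited: under Protocol 9.1 the study is positive on the primary alone. No gain was computed for Weeks 52, 76 or 104.

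**What to change.** Before Part A database lock and while the team is still blinded, make the rank ANCOVA the main Week 24 CAFS analysis, use its p-value in SAP 3.5, and keep the Wilcoxon test as the sensitivity analysis. In the text:

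- List main effects for treatment, the five randomisation factors, disease duration, baseline ALSFRS-R and baseline NfL, reconciled with SAP 3.2.3.
- State whether covariates enter raw or ranked, and whether baseline NfL is logged. SAP 3.3.1.2 specifies the log only for NfL as an outcome.
- Apply the fewer-than-10 rule of SAP 3.2.2.
- Replace a missing baseline NfL by the median pooled over arms, because the mITT definition does not require NfL. Baseline ALSFRS-R should not be missing in practice, since eligibility needs a screening score.

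The same order at Weeks 52, 76 and 104 is optional, for consistency. CAFS at those weeks gates nothing, Week 52 would need a protocol change or an entry in SAP 3.9, and the Part B dosing pause affects that comparison far more.

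The cost is a further SAP version with a short justification, a slightly less simple test, and about 1 point of power if the covariates turn out not to predict CAFS. No new data are needed. Protocol 9.4.3 leaves the detail of the other secondary analyses to the SAP, so Week 24 needs no protocol amendment.
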